**An example of how we envisage the scale with the three different response options:**

Greatest \_\_\_\_\_ / \_\_\_\_\_ / \_\_\_\_\_ least  
 very great difficulty    great difficulty    some difficulty

A. Do you find that your sight at present in some way causes you difficulty in your everyday life?

Yes, very great difficulty	Yes, great difficulty	Yes, some difficulty	No, no difficulty	Cannot decide
				

B. Are you satisfied or dissatisfied with your sight at present?

Very dissatisfied	Fairly dissatisfied	Fairly satisfied	Very satisfied	Cannot decide
				

C. Do you have difficulty with the following activities because of your sight?

If so, to what extent? In each row place just one tick in the box which you think best corresponds to your situation.

	Yes, very great difficulty	Yes, great difficulty	Yes, some difficulty	No, no difficulty	Cannot decide
Reading text in newspapers					
Recognising the faces of people you meet					
Seeing the prices of goods when shopping					
Seeing to walk on uneven surfaces, e.g. cobblestones					
Seeing to do handicrafts, woodwork etc.					
Reading subtitles on TV					
Seeing to engage in an activity/hobby that you are interested in					

## Special Report: The American Academy of Ophthalmology Task Force Consensus Statement on Adverse Events with Intraocular Lenses

In 1978, the US Food and Drug Administration approved the first investigational device exemption studies of intraocular lenses (IOLs). Outcomes were initially published in 1983 on pooled, publicly available data from IOL premarket approval studies that were used to support marketing approvals. After publication, this “historical control” information was used as a benchmark for the assessment of the safety and effectiveness of new IOLs. These

safety and effectiveness endpoints have been referred to as the “Food and Drug Administration Grid” and “Safety and Performance Endpoints” (SPEs) for IOLs. Although the SPEs were updated on the basis of additional premarket approvals in 1998, they have not been updated to reflect the development of “premium IOLs,” including toric, multifocal, accommodative, and phakic IOLs. Premium IOLs may present additional adverse events (AEs) to those already established for monofocal IOLs. Further, most of the AEs in the “Grid” do not have standard definitions, and the definitions used could have changed over time with advances in our understanding of ocular pathology. Considering untoward events associated with premium IOL implantation and that would be appropriate as safety endpoints in clinical studies of new premium IOLs, the American Academy of Ophthalmology’s Task Force has developed consensus definitions for premium IOL SPE AEs as shown in Table 1. The AE of secondary IOL intervention has been subcategorized by the type of intervention and IOL exchange, removal, and reposition. These indications are listed and defined in Table 2 and Appendix 1.

At this time, acceptable rates for premium IOL SPE AEs have not been established. However, the definitions proposed may be used during clinical studies of new IOLs going forward to allow for the determination of appropriate SPE rates that can be applied to the assessment of new premium IOLs in the future.

[name]

[name]

[name]

[name], MSEE

[name]

[name], PhD

[name]

[name], MS

[name], OD

[name]

[name]

Advanced Vision Care, Clinical Professor, David Geffen School of Medicine, Jules Stein Eye Institute, UCLA, Los Angeles, California;

## Reports

Table 1. Postoperative Adverse Event Definitions for Intraocular Lenses

Adverse Event	Definition
Chronic anterior uveitis	Persistent anterior segment inflammation characterized by grade 1+ cell or greater using SUN criteria 
Clinically significant cystoid macular edema	Macular edema diagnosed by clinical examination and adjunct testing (e.g., OCT, FA) resulting in BCDVA of $\leq 20/40$ at $\geq 1$ mo
Corneal edema	Corneal swelling (stromal or epithelial) resulting in BCDVA of $\leq 20/40$ at $\geq 1$ mo
Endophthalmitis	Intraocular inflammation requiring diagnostic vitreous tap and intraocular antibiotics
Mechanical pupillary block	Shallowing of anterior chamber due to obstruction of aqueous humor flow from the posterior to anterior chamber through the pupil by the crystalline lens, vitreous face, or implanted device
Increased IOP	Elevation of IOP by $\geq 10$ mmHg above baseline to a minimum of 25 mmHg
Rhegmatogenous RD	Partial or complete RD associated with retinal tear
Toxic anterior segment syndrome	Acute, noninfectious inflammation of the anterior segment that starts within 24 hrs after surgery, usually resulting in hypopyon and commonly presenting with corneal edema, that improves with steroid treatment
Secondary IOL intervention	
Exchange	The investigational device is replaced with the same lens model.
Removal	The investigational device is removed and replaced with a noninvestigational lens or no lens is implanted.
Reposition	The existing IOL is surgically moved to another location or rotated.

BCDVA = best-corrected distance visual acuity; FA = fluorescein angiography; IOL = intraocular lens; IOP = intraocular pressure; OCT = optical coherence tomography; RD = retinal detachment; SUN = Standardization of Uveitis Nomenclature.

Table 2. Definitions of Indications for Device Exchange, Removal, or Reposition

Indication	Definition
Capsular block syndrome	Hyper-distention of the lens capsular bag due to the IOL optic blocking egress of fluid through the anterior capsulotomy typically inducing a myopic refractive error
Cataract	Any opacification of the crystalline lens with or without reduced visual acuity
Chronic anterior uveitis	Persistent anterior segment inflammation characterized by grade $\geq 1+$ cell using SUN criteria 
Endothelial cell loss	Chronic endothelial cell loss at a rate greater than that due to normal aging
Incorrect IOL power	Postoperative refractive error different from predicted and not due to a calculation or other user error
Iris pigment epithelium loss*	New or worsening iris transillumination defects or increase in pigmented cells in the anterior chamber noted after the 1-wk visit when assessed before instillation of any dilating drops
Lens optic abnormality	Unanticipated visual outcome (e.g., acuity, contrast sensitivity, symptoms) associated with opacification, vacuoles, microvacuoles, or subsurface nanoglistenings and not due to other causes
Malpositioned IOL	Decentration, tilt, or rotation of IOL requiring reoperation May include changes induced by Nd:YAG laser anterior or posterior capsulotomy
Early	If noted before 120 days postoperatively
Late	If noted at $\geq 120$ days postoperatively
Damaged IOL	Crack of lens optic, breakage, or deformity of haptic, or other damage to the IOL May include changes induced by Nd:YAG laser anterior or posterior capsulotomy
Pupil ovalization	Progressive deformation of the pupil with elongation of the pupil in the meridian of the long axis of the IOL Documentation to be made under photopic conditions †
Pain	Graded as $\geq 4$ on the standardized pain numeric rating scale of current pain intensity from 0 (no pain) to 10 (worst possible pain)
Peripheral anterior synechiae	Progressive closure of the anterior chamber angle due to propagation of anterior synechiae in the absence of obvious anterior uveitis
Patient-reported undesirable optical phenomena	Dysphotopsia (positive or negative or both), monocular diplopia, intolerable glare, halos, or other visual symptoms, not due to 1 of the indications listed

IOL = intraocular lens; Nd:YAG = neodymium-doped yttrium aluminium garnet; SUN = Standardization of Uveitis Nomenclature.  
\*If there is a transillumination defect preoperatively, then a photograph should be taken, and then at each subsequent visit, a photograph should be taken and compared with the preoperative photograph via a standardized photographic method.  
†A consensus statement regarding a proposed methodology for standardizing assessment of pupil ovalization is available in Appendix 1.

Ophthalmology Volume 124, Number 1, January 2017

**Appendix 1. Oval Pupil Measurement Background and Standard Operating Procedure**

**Background**

The only study of the oval pupil available was by Isotani et al in 1995, who studied the ratio of the major to minor diameter in healthy subjects by using infrared photography. The subjects were dark adapted, so these are scotopic pupil measurements.

**Standard Operating Procedure**

If the clinician observes an oval or irregularly shaped pupil (dyscoria) at any visit after surgery, photographs should be taken at that visit and each subsequent visit to determine if the ovalization is progressive. The major and minor diameters of the pupil, which may not be orthogonal, are measured on the photograph, which must be taken in photopic conditions (>200 foot-candles or 2153 lux) so the pupil is maximally constricted. The pupil constriction provides the setting for pupil ovalization. For the measurement, the diameters must pass through the center of the least-squares, best-fit ellipse or centroid of the pupil perimeter. The ratio of the major to minor diameter is then calculated and reported. The photograph may be taken with any camera, including but not limited to slit-lamp cameras, topographers, and Scheimpflug devices, but the eye image must be captured under photopic conditions as specified.

**Definitions**

- Decentration of an intraocular lens (IOL) is the lateral horizontal and vertical displacement of an IOL relative to the visual axis as seen by the clinician through the cornea (subject-fixated coaxially sighted corneal light reflex, as described by Chang and Waring).
- Tilt of an IOL is the horizontal and vertical angle from perpendicular of an IOL relative to the visual axis (subject-fixated coaxially sighted corneal light reflex, as described by Chang and Waring).
- Chord length  $\mu$  is the displacement (distance) between the subject-fixated coaxially sighted corneal light reflex and pupil center. For some diffractive IOLs, the midpoint between pupil center and visual axis may be optimal.

**Tilt, Decentration, and Chord Length  $\mu$**

The goal is to measure tilt, apparent decentration through the cornea, and chord length  $\mu$  on all subjects with a premium IOL.

Table 1. Ratio of IOL Toricity to Corneal Astigmatism

	Effective Lens Position					
A-constant—>	116.346	117.203	118.059	118.916	119.773	120.630
Surge on Factor—>	0.287	0.772	1.257	1.742	2.227	2.713
ELP—>	4.000	4.500	5.000	5.500	6.000	6.500
IOL Power	Resulting Ratio of IOL Toricity to 2 D of Corneal Astigmatism					
10	1.359	1.424	1.494	1.571	1.654	1.745
22	1.277	1.330	1.387	1.450	1.519	1.595
34	1.198	1.239	1.284	1.334	1.390	1.452
46	1.121	1.151	1.185	1.223	1.267	1.316

D = diopter; ELP = effective lens position; IOL = intraocular lens.

**SAP CHANGE HISTORY**

Version	Section(s)	Page(s)	Description of Change(s)	Rationale for Change(s)
1.0	N/A	N/A	Original	N/A
2.0	2.1	2	Clarify worst-case, best-case and tipping point analysis	To address FDA considerations in letter dated February 28, 2018.
	2.1	2	Add sensitivity analysis to BCDVA endpoint	
	2.1	3	Clarify adverse event data reporting	
	2.1	3	Include all randomized subjects for accountability/enrollment/demographic tables	
	2.3 & 2.5	4	Update reference number	
	6.9	11	Add subgroup analysis, including gender	
	7	11 & 12	Clarify sample size calculation. Add sample size calculation for BCDVA and AE rate comparing to ISO SPE rate	
	8.0	13	Add 2 more references for tipping point analysis	
	Appendix I	14	Include all randomized subjects for accountability/enrollment/demographic tables	
	Appendix I	17	Add sensitivity analysis to BCDVA table	
	Appendix I	21	Add subgroup analysis, including gender	
	Footer	All pages	Change version to 2.0 in footer	

Version	Section(s)	Page(s)	Description of Change(s)	Rationale for Change(s)
2.0	Appendix	17	Add sensitivity analysis to primary DCIVA and secondary (DCNVA and spectacle wear) endpoints tables	Version 1.0 of SAP missed listing the sensitivity analysis for these tables
3.0	1, 2.5, 5.2.2, 6.9, Appendix I	1, 5, 7-8, 11, 17, 20-21	Change secondary effectiveness endpoint from spectacle wear to overall spectacle independence	Update with PRSIQv2 validation work to use composite dichotomous score for overall spectacle independence as secondary effectiveness endpoint
	2.1, Appendix I	1-3, 17	Change analysis population for overall spectacle independence endpoint	Imputation is not recommended in the PRO dossier validation. Update to remove imputation from analysis population.
	2.3, 2.5, 8.0	4, 5, 13	Update reference for the rest of the document	Delete one of the references in section 2.1 due to the removal of MI analysis for overall spectacle independence endpoint. Update the numbering of the references for the rest of the document
	2.5	4-5	Clarify multiplicity adjustment for primary endpoints	Clarify multiplicity adjustment for primary endpoint; only DCIVA endpoint requires hypothesis testing.
	Appendix II	23-24	Add contrast sensitivity conversion formula	Previous version missed contrast sensitivity conversion formula
	Appendix III	25	Add algorithm for constructing overall spectacle independence variable	Update with PRSIQv2 validation work to use composite dichotomous score for overall spectacle independence as secondary effectiveness endpoint
	Footer	All pages	Change version to 3.0 in footer	Reflect correct version number

## 1 INTRODUCTION

This document summarizes the statistical methods to be implemented during the analysis of data for the TECNIS® 1-Piece aspheric acrylic intraocular lens (IOL), Model ZHR00 (SUR-IOL-652-2001) study. This study will be a 6-month, prospective, multicenter, bilateral, subject/evaluator-masked, randomized clinical trial conducted at up to 10 sites. Subjects will be bilaterally implanted with either the Model ZHR00 IOL or the control Model ZCB00 IOL. Up to 264 subjects will be enrolled to achieve approximately 224 subjects randomized and bilaterally implanted, resulting in approximately 200 evaluable subjects (100 in the study arm and 100 in the control arm) at 6 months.

The key time point for reporting and submitting the PMA supplement will be at 6 months. The primary effectiveness endpoints for this study are mean (LogMAR) monocular distance corrected intermediate visual acuity (DCIVA) under photopic conditions, at a fixed distance (66 cm) and monocular distance-corrected defocus curve at 6-months postoperative.

The secondary effectiveness endpoints are mean (LogMAR) monocular distance corrected near visual acuity (DCNVA) at 40 cm, and overall spectacle independence at 6-months postoperative.

The safety endpoints are monocular best corrected distance visual acuity (BCDVA) non-inferior to control, the rates of adverse events compared to ISO 11979-7 SPE (safety and performance endpoints) including SSI due to optical issues causing visual symptoms, contrast sensitivity and visual symptoms via PRO questionnaire evaluated at 6 months.

Other key endpoints include binocular defocus curve testing, other visual acuity, refractive data, medical findings, lens findings, ocular/visual symptoms (non-directed), fundus visualization, subject satisfaction and other questionnaire responses.

## 2 ANALYSIS POPULATIONS

### 2.1 ANALYSIS POPULATIONS/HANDLING OF MISSING DATA

The primary analysis population for the primary DCIVA and secondary DCNVA endpoints will be a modified Intent-to-Treat (mITT) analysis for all first-eyes randomized and implanted with either a test or control study IOL. Sensitivity analyses using all randomized subjects will be performed as described below. Since the PRO dossier does not recommend imputation and the validation work for the PRO dossier was based on complete data set (i.e., with non-missing value) for each composite dichotomous score, overall spectacle independence endpoint will follow the guideline of PRO dossier and only use non-missing values for analysis. Therefore, the primary analysis

population for overall spectacle independence will be the safety population (SP) with subjects who are bilaterally implanted with the same study lens in both eyes. For all subjects with missing data for the spectacle independence endpoint at the 6-month visit, information (e.g., percentage missing, reason for missing data, etc.) will be provided. There are no inferential statistics for the defocus curve primary endpoint; therefore, safety population (SP) will be the primary analysis population for this endpoint. The mITT population will be used for the statistical success criterion of the primary DCIVA endpoint and secondary effectiveness endpoint DCNVA where SP will be used for the clinical success criterion of those endpoints since there is no inferential statistics comparison for the clinical success criterion. The primary analysis population for all safety endpoints will be the safety population. The key timeframe for the study endpoint will be at 6-months postoperative visit unless states otherwise.

For eyes that do not have data available at the 6-month postoperative visit, other than PRSIQv2, data will be imputed for the mITT analyses. For continuous variables (DCIVA and DCNVA), planned method to use is the MCMC full-data imputation as described in Little & Rubin. Data imputation and analysis will be performed using the MI and MIANALYZE procedures in SAS® (Version 9.4).

In addition to the above imputation methods, sensitivity analyses using different imputation approaches (worst-case scenario, best-case scenario and tipping point) will also be performed for primary DCIVA and secondary DCNVA and for the safety endpoint of mean BCDVA. These analyses will be performed using all randomized subjects with the IOL group based on the randomization. A worst-case scenario will be performed with the worst score (poorest visual acuity value from all first eyes) assigned to missing data for the test IOL and the best score (best visual acuity value from all first eyes) assigned to missing data for the control IOL. A best-case scenario will also be performed, assigning the best value (best visual acuity value from all first eyes) to missing test IOL data and the worst value (poorest visual acuity values from all first eyes) to missing control IOL data. A tipping point analysis will also be performed if more than 10% of mITT population is missing at the 6-month visit. The tipping point analysis for visual acuity endpoints (DCIVA and DCNVA) will be evaluated using shift parameters of 0 to 0.30 LogMAR in 0.05 LogMAR increments with these shift parameter values adjust the imputation values for the test IOL group. This results in evaluating significance using missing test IOL data that is from 0 to 3 lines worse than imputed values.

A Per-Protocol (PP) analysis will also be used for primary effectiveness and secondary endpoints. The PP population for monocular data will include eyes with a test or control lens implanted, evaluated within the proper study interval and without clinically-relevant protocol deviations (deviations that could potentially impact the primary or secondary endpoints) as determined prior to database lock. The PP population for binocular data

will include subjects that do not have any of the deviations stated above in either eye. PP tables will include available data at the time of analysis.

The safety population will consist of all eyes and subjects implanted with either a test or control IOL(s) and with data available at the time of analysis (i.e., no data imputation). Reporting of cumulative complications and cumulative adverse event (occurring at any time postoperative either at standard visits or interim visits) will include data from all study eyes implanted. Thus, all adverse events at any postoperative visit (including standard or interim visit) will be reported unless it is results at a given visit (i.e., 6 months). For all safety endpoints, only the safety population will be used. For BCDVA, a best-case population will also be used, consisting of eyes in the safety population without any clinically-relevant preoperative ocular pathologies or macular degeneration detected at any time.

For the primary DCIVA, and secondary DCNVA, the mITT, PP and safety populations will be used for data reporting. For the defocus curve primary endpoint and overall spectacle independence secondary endpoint, only safety and PP populations will be used for data reporting. For safety endpoints and other endpoints, only the safety population will be used. The primary analysis will be based on first-eye data, unless stated otherwise. However, select data such as some visual acuity variables will also be reported separately for second eyes as supportive data only. Binocular data will be reported for those who are implanted with the same (test or control) IOL in both eyes. For demographics/enrollment/accountability data will also be reported for all randomized subjects whether an IOL was implanted or not with group assignment based on the randomization. Appendix I lists the analysis tables including the endpoints and the populations used to report the results.

## **2.2 VISIT WINDOWS**

Subject visits will occur at Preoperative for both eyes, Operative, 1 day, 1 week and 1 month for each eye, and 6 months for both eyes together. The exact number of days for each interval is described in the protocol. The number of eyes with missing visits or data outside of the visit interval will be reported.

## **2.3 DATA CONVENTIONS**

Descriptive statistics will typically include sample size (N), mean, standard deviation (SD), median, minimum (Min.), and maximum (Max.) as appropriate for continuous variables. For categorical data, the frequency and proportion will be computed.

For continuous variables, statistical tests assuming normality will generally be used. However the data will be reviewed to evaluate whether the normality assumption is appropriate. If it is found not to be appropriate, either an appropriate transformation of the data (i.e., logarithmic) may be used or the corresponding non-parametric tests may

be used. Deviations from the proposed statistical guidelines will be substantiated by sound statistical rationale. For categorical data, Fisher's exact test will be used for comparison between IOL groups. Comparisons for ordinal data will be done using the Wilcoxon rank-sum test.

Unless otherwise indicated, alpha will be set to 0.05 for two-sided statistical testing with alpha set to 0.025 for one-sided testing. See Section 2.5 Multiplicity Adjustment below for the primary and secondary endpoints related to product claims.

For visual acuity data, letter scores will be converted to LogMAR prior to analysis. Formulas used for visual acuity analysis are included in Appendix II. For refractive data, all values will be converted to plus cylinder with sphere adjusted for infinity. Formulas used for refractive data are also included in Appendix II.

## **2.4 RANDOMIZATION**

A randomization list will be created by a JJSV biostatistician for each investigational site and the randomization code will be uploaded into the electronic data capture system (EDC). Subjects will be randomized to the investigational Model ZHR00 IOL or the Model ZCB00 control IOL. Unmasked study personnel at the site will be trained to the randomization process through the EDC system and will randomize subjects after the subject has signed the informed consent form, has met all eligibility criteria and the investigator has documented which eye will be the first implanted.

If a surgeon implants the wrong study lens, i.e., other than the one on the randomization schedule, the subject's study data will be analyzed according to the randomization schedule in the mITT population and will be analyzed according to the lens received in the safety population. The subject will be excluded from the Per-Protocol population analysis. If a surgeon implants a non-study IOL (e.g., due to capsule rupture prior to IOL implantation) or if the surgery is canceled in the few days between randomization and surgery (e.g., due to death, illness), the subject will not be part of the mITT, safety or Per-Protocol populations but will be placed in the intended IOL group (IOL group based on randomization schedule) and included in the worst case/best case sensitivity analyses.

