### SURGICAL COMPLICATIONS

Should a surgical complication occur, implantation of a study lens will be at the investigator's discretion. In the event of capsular bag or zonular rupture, the lens should not be implanted if the complication may result in lens instability. Additionally, the lens is not to be implanted in the sulcus. In this case, the investigator may implant his/her choice of a back-up, non-investigational IOL. The subject should be exited from the study if a non-study lens is implanted as a result of a surgical complication during the first-eye implantation; however, the eye will be followed until resolution of the complication prior to exiting the subject. Should a surgical complication occur during the second-eye surgery and result in implantation of a non-study lens, the subject will not be exited from the study; the first eye will continue to be followed per-protocol, although data may be analyzed separately, and the second eye will be followed for safety until resolution of the complication.

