## **10.8 EXIT OF SUBJECTS**

An Exit CRF will be completed for all subjects, either when they complete the study or if they exit early.

It is the responsibility of the investigator to provide complete follow-up data to JJSV for each subject, and every attempt should be made to gather that complete follow-up data for all subjects enrolled, as missing data can have a negative effect on the study results. Patients who would be traveling, relocating or otherwise unavailable for postoperative follow-up visits should not be enrolled in this clinical study.

A subject will be considered a "screen failure" if he/she does not meet the eligibility criteria or if consent is withdrawn prior to randomization.

A subject will be considered "discontinued prior to treatment" if the subject is randomized but does not undergo surgery or receive a study lens for various reasons including: the planned implant being aborted due to surgical complications, the subject withdrawing consent prior to treatment or the subject died prior to treatment.

Subjects will be "discontinued" from the study if one study lens (if implanted unilaterally) or both study lenses (if implanted bilaterally) are removed or if the subject dies.

If a subject receives at least one study lens, he/she is to be followed according to the schedule in Table 2 (Section 10.2) for visit windows.

Subjects will be considered “lost-to-follow-up” from the study only if irretrievably lost for unavoidable reasons such as: subject moved/unable to locate, subject ill/unable to travel, subject uncooperative/refuses further study participation. In the event of subject relocation, effort must be made by the investigator to secure follow-up information (i.e., slit-lamp findings and general visual acuity, etc.) from the subject’s new physician.

If a subject is exited early from the study, the investigator must indicate the reason for study exit on the CRF. In the event of a lens removal or other serious adverse event, the subject may be exited from the study; however, effort must be made by the investigator to follow the subject until resolution of the adverse event before exiting the subject from the study.

Following study completion or early exit, subjects will be informed about which lens model they received. Additionally, all study subjects are to be instructed to undergo regular eye examinations at least yearly and also to return to their doctor if any eye complications are experienced.

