	First Eyes	First Eyes	Second Eyes	Second Eyes	Subjects	Subjects	Comments (population used for analysis)
	ZHR00	ZCB00	ZHR00	ZCB00	ZHR00	ZCB00	
Operative Data							
General Surgical Parameters: No. and Percent with each response	X	X	X	X			SF
Incision type (by type) Incision size in mm (<2.6, 2.6 to 2.7, 2.8 to 3.0, >3.0) Capsulorhexis diameter in mm (≤4.0, 4.1 to 5.0, >5.0) Capsulorhexis centration (centered/eccentric) Capsulotomy method (by type) Lens Removal Method (by method) Viscoelastic agent (by type) Implant instrument (by type) Lens placement (capsular bag, other) Type of closure (sutureless, suture)							
Surgical Complications: No. and percent with each response	X	X	X	X			SF
Surgical complications (none, all items listed on CRF, other) Other surgical procedures (none, all items listed on CRF, other)							
Lens Power Implanted (N, Mean, SD , Median, Min., Max. in Diopters (D))	X	X	X	X			SF

	First Eyes	First Eyes	Second Eyes	Second Eyes	Subjects	Subjects	Comments (population used for analysis)
	ZHR00	ZCB00	ZHR00	ZCB00	ZHR00	ZCB00	
PRIMARY EFFECTIVENESS ENDPOINTS							
Monocular DCIVA at 66cm (LogMAR) at 6M (N, Mean, SD, Median, Min., Max., 95% CI)	X	X	X	X			miITT/SF/PP/Sensitivity-1 st eyes (SF-2 nd as supportive data only)
Monocular defocus curve at 6M	X	X					SF/PP
SECONDARY EFFECTIVENESS ENDPOINTS							
Monocular DCNVA at 40cm (LogMAR) at 6M (N, Mean, SD, Median, Min., Max., 95% CI)	X	X	X	X			miITT/SF/PP/Sensitivity-1 st eyes (SF-2 nd as supportive data only)
Overall Spectacle independence at 6M (No. and percent of the response)					X	X	SF/PP bilateral subjects
SAFETY ENDPOINTS							
Monocular BCDVA (LogMAR) at 6M (N, Mean, SD, Median, Min., Max., 90% CI)	X	X	X	X			SF - 1 st eyes Sensitivity - 1 st eyes (SF-2 nd as supportive data only)
The number and percent of eyes with adverse events as described in ISO11979-7	X	X	X	X			SF - 1 st eyes (SF-2 nd as supportive data only)
Monocular contrast sensitivity at 6M (N, Mean, SD, Median, Min., Max., 90% CI)	X	X					SF
Ocular visual symptoms via questionnaire at 6M					X	X	SF
OTHER ENDPOINTS							
Visual Acuity – Intermediate							
Monocular DCIVA at 66cm (LogMAR) at 6M by Site (N, Mean, SD, Median, Min., Max.)	X	X					SF

	First Eyes	First Eyes	Second Eyes	Second Eyes	Subjects	Subjects	Comments (population used for analysis)

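### Operative complications that prevent implantation of the study lens are followed up but appear in no planned complication or adverse-event table

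*SAP*

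**What the plan says.** SAP 2.4 covers randomised subjects who do not get a study lens. One trigger is worded "If a surgeon implants a non-study IOL (e.g., due to capsule rupture prior to IOL implantation", with the bracket closing there; the other is surgery cancelled after randomisation. In either case "the subject will not be part of the mITT, safety or Per-Protocol populations but will be placed in the intended IOL group", and the subject is "included in the worst case/best case sensitivity analyses". SAP 2.1 defines those sensitivity analyses for DCIVA, DCNVA and mean BCDVA only.

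SAP 2.1 limits the safety population to eyes and subjects that received a test or control lens, and uses only that population for the safety endpoints. Cumulative complication and adverse-event reporting "will include data from all study eyes implanted". Protocol 20.1 says the same. SAP 2.1 extends reporting to all randomised subjects only for demographics, enrolment and accountability.

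In Appendix I the operative row "Surgical complications (none, all items listed on CRF, other" is marked SF (safety population). So are the ISO adverse events, medical and lens findings, both adverse-event listings, the adverse-event table, non-ocular serious events and non-adverse-event procedures.

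Protocol 10.6 (Surgical Complications) says that, when a complication puts a non-study lens in the first eye, "the eye will be followed until resolution of the complication prior to exiting the subject". When this happens in the second eye, the subject stays in the study and the second eye is followed for safety. Protocol 10.8 gives "the planned implant being aborted due to surgical complications" as one reason for classing a subject as discontinued before treatment, so the case was foreseen.

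**The concern.** The operative case report form records surgical complications and serious or device-related events, and Protocol 11.3 requires every adverse event to be reported to the sponsor. The information therefore exists. Under the population rules, a complication mild enough to allow implantation is tabulated, and one severe enough to prevent it is not. A complication table whose membership depends on how the complication turned out is conditioned on its own outcome.

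At stake is the completeness of the operative safety account. Randomisation precedes surgery, the surgeon knows the assigned lens (Protocol 10.4), and implantation after a complication is left to the investigator within limits (Protocol 10.6). If eyes were lost unequally between arms, no planned complication table would show it.

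**Working it through.** **1. Tracing one eye.** Take a randomised first eye with a capsule rupture before the lens is inserted, which then receives a non-study lens.
- Data capture: the complication goes on the operative form and the eye is followed until it resolves (Protocol 10.6).
- Safety population: excluded by name in SAP 2.4, and also by the definition in SAP 2.1.
- Surgical Complications and all adverse-event outputs in Appendix I: marked SF, so excluded.
- Accountability, enrolment and demographics: included, as a randomised subject. These show the discontinuation, not the complication.
- Worst-case/best-case analyses: included, with an assigned acuity value. These carry no complication data.

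An eye left with no lens is not named in SAP 2.4 but falls outside the SAP 2.1 definition. An aborted second eye also falls outside the implanted eyes. Read literally, the subject-level wording of SAP 2.4 would drop the whole subject, whereas Protocol 10.6 keeps that subject in the study and continues to follow the first eye.

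**2. Denominator.** SAP 7.4 gives 200/0.9 = 222.2, raised to 224 randomised, and 224/0.85 = 263.5, raised to 264 enrolled. Both figures reproduce. Per arm this is 224/2 = 112 first eyes; the trial plans 224 × 2 = 448 surgeries.

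**3. Expected number omitted.** The documents give no rate *p* of aborted implants per eye, so 0.25% to 3% is an assumption. The expected count is n·p, and the chance of at least one is 1 − (1 − p)^n.

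| Assumed p | First eyes per arm, 112p | At least one ZHR00 first eye, 1 − (1 − p)^112 | At least one first eye in trial, 1 − (1 − p)^224 | All eyes in trial, 448p |
|---|---|---|---|---|
| 0.25% | 0.28 | 24% | 43% | 1.1 |
| 0.5% | 0.56 | 43% | 67% | 2.2 |
| 1% | 1.12 | 68% | 89% | 4.5 |
| 2% | 2.24 | 90% | 99% | 9.0 |
| 3% | 3.36 | 97% | 99.9% | 13.4 |

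**4. Effect on the reported rate.** Suppose k of 112 first eyes in an arm are aborted because of a complication, and m implanted eyes also have one. The plan reports m/(112 − k); all attempted surgeries give (m + k)/112. The difference is k(112 − k − m)/[112(112 − k)]. It is positive unless every implanted eye has a complication, and it is largest at m = 0, where it equals k/112. The understatement is thus at most 1/112 = 0.9%, 2/112 = 1.8% or 3/112 = 2.7% for one, two or three aborted eyes.

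**The case against.** The strongest reply is that a safety population defined by exposure is conventional and suits the device question. The formal adverse-event test sets ZHR00 first eyes against a fixed ISO rate (SAP 5.3.2), and cumulative reporting concerns postoperative events. Putting eyes that hold another lens into that denominator would blur it. This stands, and it is why the safety population should be left alone. It does not answer the point about the Surgical Complications table, which describes the operation rather than exposure to the lens.

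Four stronger readings are tempting, and the documents do not support them.
- A reader might infer that these subjects vanish from reporting. They do not: they are in the all-randomised tables and the acuity sensitivity analyses, and an exit form is completed for each. Adverse events go to the sponsor, and to the IRB under its own requirements; the medical monitor reviews serious and device-related events. The gap is in tabulation, not in oversight.
- A reader might infer that a rupture during an attempted insertion is certainly excluded. The SAP 2.4 example is a rupture before implantation, and the text does not settle how to class a study lens inserted and removed in the same operation.
- A reader might infer bias between arms. An unmasked surgeon with some discretion makes a difference possible. However, Protocol 10.6 states limits on implantation that apply to both lenses, the two lenses share material, general dimensions and implantation systems, and nothing in the documents shows that either would be abandoned more readily.
- A reader might infer that a success criterion or the ISO test is affected. None is shown to be. SAP 4 plans between-group comparisons of operative parameters, but no success criterion rests on them.

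The objection that few eyes are involved also has force. Eligibility excludes capsular and zonular abnormalities, and at 0.25% it is more likely than not that no ZHR00 first eye is affected.

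**Conclusion.** The point holds as a limited reporting gap. The population rule and the Appendix I assignments are explicit, and no planned complication or adverse-event output covers eyes in which surgery was started but no study lens was implanted. The Surgical Complications table therefore understates operative complications whenever such an eye occurs.

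The size rests wholly on the assumed abort rate, and even the low end of 0.25% is an assumption rather than a figure from the documents. Over the assumed range the omission is about 0.3 to 3.4 first eyes per arm. The calculation treats eyes as independent with a common rate. Confidence is high on the population rule and low on the number of eyes.

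This is worth correcting because the data are already collected and the correction is cheap. It does not threaten the trial's conclusions.

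**What to change.** - Keep the safety population, the ISO denominators and the acuity populations as they are.
- Add to SAP 2.1 and Appendix I a separate table or listing of surgical complications, operative adverse events and their outcomes. It should cover all randomised eyes in which surgery was started, by assigned lens, with first and second eyes shown separately.
- Include a row for eyes in which the study lens was not implanted, or was removed during the same surgery. This also makes the unsettled insertion-and-removal case visible.
- Keep this output apart from the safety-population tables, because SAP 2.4 groups wrong-lens subjects there by lens received.
- Reconcile the subject-level exclusion in SAP 2.4 with Protocol 10.6, which retains a subject when only the second eye receives a non-study lens.

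The cost is SAP wording and one additional output, with no new data collection. The downside is that reported operative complication rates may be slightly higher.
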